10.9.1 Informed consent

The participant or their legally authorized representative should be verbally informed prior to initiating any changes that are to be implemented for the duration of the emergency (eg. study visit delays/treatment extension, use of local labs).

10.9.2 Study procedures

Attempts should be made to perform all assessments in accordance with the approved protocol to the extent possible. If onsite visits are possible and there is a need to reduce the time spent on site to a minimum, the focus should be on IMP infusion/administration, collection of safety information (vital signs, adverse events) and safety blood collection (mainly biochemistry, hematology and ADA, if planned for the visit). However, all efforts should be made to perform the measurements of key parameters for efficacy endpoints, namely CT/MRI scan and tumor tissue collection for this study.

If onsite visits are not possible due to a temporary disruption caused by an emergency, focus should be given to assessments necessary to ensure the safety of participants and those important to preserving the main scientific value of the study.

- Remote visits (eg, with home nurses, home health vendor, etc.) may be planned for the collection of possible safety and/or efficacy data.
- Visit windows may be extended for assessment of safety and/or efficacy data that cannot be obtained remotely.
- Use of local clinic or laboratory locations may be allowed.

10.9.3 Statistical analysis

The impact of any regional or national emergency declared by a governmental agency on study conduct will be summarized (eg, study discontinuation or discontinuation/delay/omission of the intervention due to the emergency). Any additional analyses and methods required to evaluate the impact on efficacy (eg, missing data due to the emergency) and safety will be detailed in the SAP.

10.9.4 Temporary discontinuation

Study intervention must be administered intravenously and at study site under the responsibility of the Investigator. Consequently, for participants who have started treatment but are unable to come to the site, administration of study intervention must be paused until regular study visits can be safely resumed at the study site.

In the event of disruption of the clinical trial due to an epidemic/pandemic (eg COVID-19), reinitiation of IMP can only occur once the Investigator has determined, according to his/her best judgement, that the contribution of the IMP(s) to the occurrence of the epidemic event (eg. COVID-19) was unlikely.

Contingencies implemented due to emergency will be documented.

10.10 APPENDIX 10: RISK ASSESSMENT

The information shown in [Table 8](#) reflects the clinical safety data available at the time of Edition 4 of the SAR444245 IB. Please always refer to the latest version of the IB for the most up-to-date safety data.

Table 8 - Risk assessment

Potential risk of clinical significance	Summary of data/rationale for risk	Mitigation strategy
Study intervention(s)		
Infusion-related reactions	SAR444245 Not observed in non-clinical toxicology studies. A minority of patients in the THOR-707-101/HAMMER study have reported such AE as detailed in the IB.	SAR444245 Standard pre-medication Dose modification and treatment guidelines for SAR444245 infusion-related reactions are provided in the individual substudy.
Hypersensitivity, including anaphylaxis	SAR444245 Not observed in non-clinical toxicology studies. No reports of anaphylaxis in the HAMMER study to date.	Exclusion of participants with known hypersensitivity to or contraindication any components of SAR444245, PEG, or pegylated drugs.
Infections	SAR444245 Nonclinical data do not indicate higher risk for infections. Adverse events of infections have been reported in the HAMMER study and are presented in the SAR444245 IB.	Routine mitigation: Participants must have appropriate ANC and other organ/bone marrow function to be included. During treatment, regular hematology and biochemistry is examined. Signs and symptoms of infection are monitored as part of TEAE.
Cytokine release syndrome	SAR444245 No major increases in cytokines have been reported in non-clinical toxicology studies. A minority of patients in the HAMMER study have reported such AE as detailed in the IB.	Study to be conducted at sites experienced with CRS management, with bed available in ICU. Premedication with paracetamol, diphenhydramine (or equivalent medications). Hydration guidelines, including management of anti-hypertensive treatment around the time of infusion, are provided. Extensive post-dosing monitoring will be performed. Dose modification and treatment guidelines are provided in the individual substudy.
Capillary leak syndrome (CLS) / Vascular leak syndrome (VLS)	SAR444245 Not observed in non-clinical toxicology studies. None reported in the HAMMER study.	Intensive monitoring in C1D1 and beyond in the first cycle. Participants are monitored for signs and symptoms of VLS. Dose modification and treatment guidelines are provided in the individual substudy.
Hematological/bone marrow toxicity	SAR444245 In 28-day repeat-dose study of IV SAR444245 in non-human primates, SAR444245-related changes in clinical	Routine mitigation: Participants must have appropriate ANC and other organ/bone marrow function to be included.

Potential risk of clinical significance	Summary of data/rationale for risk	Mitigation strategy
	
pathology parameters were observed at all doses and were generally most prominent 3 days following each dose. Changes in hematology parameters included decreased or attenuated reticulocytes followed by decreases in red blood cell (RBC) mass at █ mg/kg/dose, and increased WBCs (lymphocytes and monocytes) and transiently mildly decreased platelets at █ mg/kg/dose. The increases in lymphocytes were attributed to the expected pharmacology of SAR444245 and correlated with the gross and microscopic findings of splenic and lymph node enlargement and increased lymphoid cellularity; there were no microscopic or clinical correlates for the decreases in platelets.
 
Adverse events of bone marrow toxicity have been reported in the HAMMER study and are presented in the SAR444245 IB. Transient lymphopenia has also been observed.
	
During treatment, regular hematology and biochemistry is examined.
 
Dose modification/discontinuation of IMP for Grade 3/4 anemia, thrombocytopenia and/or neutropenia as per general guidelines for the management of TRAEs (see Section 6.5.3 in the individual substudy).

Hepatotoxicity	
SAR444245
 
In 28-day repeat-dose study of IV SAR444245 in mice, males at █ mg/kg/dose and females at █ and █ mg/kg/dose also had mild increases in AST and ALT activity that corresponded to a spectrum of microscopic findings in the liver including mononuclear cell infiltration, apoptosis, necrosis, mixed leukocyte inflammation, oval cell hyperplasia, and Kupffer cell hypertrophy.
 
No such data are reported in 28-day Repeat-Dose Study of IV SAR444245 in non-human primates.
 
A minority of patients in the HAMMER study have reported such AE as detailed in the IB.
	
Patients with significant impaired liver functions are excluded.
 
Monitor clinical signs and symptoms of hepatic impairment as part of TEAE.
 
Monitor liver function parameters (AST, ALT, bilirubin & ALP) regularly from screening and throughout the study.
 
Dose modification and treatment guidelines for liver enzyme increase are provide under immune-related reactions in the individual substudy.

Nephrotoxicity	
SAR444245
 
There are no non-clinical data indicating a potential for nephrotoxicity.
 
One relevant serious adverse event (SAE) considered related to SAR444245 (Acute Kidney Injury) has been reported in the HAMMER study within a monotherapy cohort.
 
Investigator's assessment is that it is related to the CRS occurring in the same patient.
 
Sponsor's assessment was that the kidney injury was related to increased fluid losses from persistent fever.
	
Participants must have appropriate eGFR to be included.
 
Monitor renal function parameters (BUN/urea & creatinine) regularly from screening and throughout the study.
 
Dose modification and treatment guidelines for nephrotoxicity are provide under immune-related reactions in the individual substudy.

Potential risk of clinical significance	Summary of data/rationale for risk	Mitigation strategy

Cardiovascular effects, including QT interval prolongation	
SAR444245
 
In 28-day repeat-dose study of IV SAR444245 in non-human primates, there were no SAR444245-related changes to the PR or QRS intervals or the heart rate (HR) corrected QTca interval. There was a SAR444245-related, dose dependent, non-adverse higher HR at doses of \geq █ mg/kg/dose beginning on Day 1 compared to the control dose group and persisting through each respective dose following applicable telemetry recording sessions, with recovery. There was also an expected physiologic inverse relationship in the respiration rate (RR) intervals as well as the raw QT intervals, which correlated to the changes in HR, and were also considered to be non-adverse. There were increases in individual females of troponin I minimal post first dose. There were marked decreases in females and males.
 
These changes correlated with findings of mononuclear cell infiltrates and/or myocardial degeneration. All changes however, recovered by the end of a 28 day or 42/44 day treatment free period.
 
A minority of patients in the HAMMER study have reported such AE as detailed in the IB.
	
Routine mitigation:
 
Selection of qualified investigative centers with availability of intensive critical care/equipment.
 
Exclusion of patients with severe or unstable cardiac condition within 6 months prior to starting study treatment, see E10 for details.
 
ECG, LVEF, and vital sign monitoring and coagulation tests performed at screening and thereafter as clinically indicated.
 
Blood pressure and vital signs monitored closely during hospitalization in safety run-in. For subsequent cycles, monitoring will depend on site assessment of participant's symptoms.

Immune-mediated Adverse Events	
SAR444245
 
A minority of patients in the HAMMER study have reported such AE as detailed in the IB.
	
Exclusion of participants with:
 
Active, known, or suspected autoimmune disease that has required systemic treatment in the past 2 years (ie, with use of disease modifying agents,

Potential risk of clinical significance	Summary of data/rationale for risk	Mitigation strategy
Risks related to special populations		
Pregnancy and lactation exposure and outcomes	SAR444245	Exclusion of participants who are pregnant or breastfeeding or expecting to conceive or father children within the projected duration of the trial as per inclusion criterion I05.
Use in children	The safety and efficacy of the study interventions in children below 18 years of age have not yet been established.	
Participants over 75 years of age	SAR444245	No specific mitigation strategy for this population.
Clinically significant medication errors	With the increased complexity of the design of oncology clinical trials, medication errors need to be considered. Although their occurrence is estimated to be low (eg, chemotherapy errors occur at a rate of about one to four per 1000 orders), their impact may be high. According to the report on medication safety in cancer clinical trials, the processes in which the errors originated were prescribing (47%), administering (10%), dispensing (6%), and monitoring (5%). Prescribing errors typically arise from not following an institutional procedure or the protocol (39%, most likely due to the protocol procedures differing from existing standards of care), followed by the written order (30%), and poor communication involving both the healthcare team and the patient (26%)	Strict adherence to the protocol. Adequate and verified training of staff at investigational sites.

Potential risk of clinical significance	Summary of data/rationale for risk	Mitigation strategy
(33,34,35).		
Overdose and its treatment	There is no specific antidote for overdose with SAR444245.	Strict adherence to the protocol; Adequate and verified training of staff at investigational sites. See Section 6.7
Study procedures		
Biopsies of tumor tissue are expected during the trial.		Strict adherence to the guidance in the protocol

10.11 APPENDIX 11: ASTCT ASSESSMENT FOR ICANS AND CRS

Table 9 - Encephalopathy assessment ICE tool for ICANS Grading

Immune Effector Cell-Associated Encephalopathy (ICE) Assessment	Number of points
Orientation: Orientation to year, month, city, hospital	4 points
Naming: ability to name 3 objects (eg, point to clock, pen, button)	3 points
Following commands: ability to follow simple commands (eg, "Show me 2 fingers" or "Close your eyes and stick out your tongue")	1 point
Writing: ability to write a standard sentence (eg, "Our national bird is the bald eagle")	1 point
Attention: ability to count backwards from 100 by 10	1 point

Source: [\(1\)](#).

Table 10 - ASTCT ICANS consensus grading for adults

Neurotoxicity domain	Grade 1	Grade 2	Grade 3	Grade 4
ICE score ^a	7-9	3-6	0-2	0 (participant is unrousable and unable to perform ICE).
Depressed level of consciousness ^b	Awakens spontaneously	Awakens to voice	Awakens only to tactile stimulus	Participant is unarousable or requires vigorous or repetitive tactile stimuli to arouse. Stupor or coma.
Seizure	N/A	N/A	Any clinical seizure focal or generalized that resolves rapidly or nonconvulsive seizures on EEG that resolve with intervention.	Life-threatening prolonged seizure (>5 min); or Repetitive clinical or electrical seizures without return to baseline in between.
Motor findings ^c	N/A	N/A	N/A	Deep focal motor weakness such as hemiparesis or paraparesis.
Elevated ICP cerebral edema	N/A	N/A	Focal/local edema on neuroimaging ^d	Diffuse cerebral edema on neuroimaging; decerebrate or decorticate posturing; or Cranial nerve VI palsy; or Papilledema; or Cushing's triad.

ICANS grade is determined by the most severe event (ICE score, level of consciousness, seizure, motor findings, raised ICP/cerebral edema) not attributable to any other cause; for example, a patient with an ICE score of 3 who has a generalized seizure is classified as grade 3 ICANS.

a A patient with an ICE score of 0 may be classified as Grade 3 ICANS if awake with global aphasia, but a patient with an ICE score of 0 may be classified as Grade 4 ICANS if unrousable.

b Depressed level of consciousness should be attributable to no other cause (eg, no sedating medications).

c Tremors and myoclonus associated with immune effector cell therapies may be graded according to CTCAE V5.0, but they do not influence ICANS grading.

d Intracranial hemorrhage with or without associated edema is not considered a neurotoxicity feature and is excluded from ICANS grading. It may be graded according to CTCAE V5.0.

Abbreviations: ASTCT=American Society for Transplantation and Cellular Therapy; CTCAE = Common Terminology Criteria for Adverse Events; EEG = Electroencephalogram; ICANS = Immune effector cell-associated neurotoxicity syndrome; ICE = Immune Effector Cell-Associated Encephalopathy; ICP = Intracranial pressure;

N/A = Not applicable.

Source: (1).

Table 11 - ASTCT ICANS consensus grading for children

Neurotoxicity domain	Grade 1	Grade 2	Grade 3	Grade 4
ICE score for children age > 12 years ^a	7-9	3-6	0-2	0 (participant is unrousable and unable to perform ICE).
CAPD score for children age < 12 years	1-8	1-8	≥9	Unable to perform CAPD
Depressed level of consciousness ^b	Awakens spontaneously	Awakens to voice	Awakens only to tactile stimulus	Unarousable or requires vigorous or repetitive tactile stimuli to arouse. Stupor or coma.

Neurotoxicity domain	Grade 1	Grade 2	Grade 3	Grade 4
Seizure (any age)	N/A	N/A	Any clinical seizure focal or generalized that resolves rapidly or nonconvulsive seizures on EEG that resolve with intervention.	Life-threatening prolonged seizure (>5 min); or Repetitive clinical or electrical seizures without return to baseline in between.
Motor weakness (any age) ^c	N/A	N/A	N/A	Deep focal motor weakness such as hemiparesis or paraparesis.
Elevated ICP/ cerebral edema (any age)	N/A	N/A	Focal/local edema on neuroimaging ^d	Decerebrate or decorticate posturing, cranial nerve VI palsy, papilledema, Cushing's triad, or signs of diffuse cerebral edema on neuroimaging

ICANS grade is determined by the most severe event (ICE or CAPD score, level of consciousness, seizure, motor findings, raised ICP/cerebral edema) not attributable to any other cause. Baseline CAPD score should be considered before attributing to ICANS.

a A patient with an ICE score of 0 may be classified as Grade 3 ICANS if awake with global aphasia, but a patient with an ICE score of 0 may be classified as Grade 4 ICANS if unrousable.

b Depressed level of consciousness should be attributable to no other cause (eg, no sedating medications).

c Tremors and myoclonus associated with immune effector cell therapies may be graded according to CTCAE V5.0, but they do not influence ICANS grading.

d Intracranial hemorrhage with or without associated edema is not considered a neurotoxicity feature and is excluded from ICANS grading. It may be graded according to CTCAE V5.0.

Abbreviations: ASTCT=American Society for Transplantation and Cellular Therapy; CTCAE = Common Terminology Criteria for Adverse Events; EEG = Electroencephalogram; ICANS = Immune effector cell-associated neurotoxicity syndrome; ICE = Immune Effector Cell-Associated Encephalopathy; ICP = Intracranial pressure;

N/A = Not applicable.

Source: (1).

Table 12 - ASTCT CRS consensus grading

CRS parameter	Grade 1	Grade 2	Grade 3	Grade 4
Fever ^a	Temperature $\geq 38^{\circ}\text{C}$	Temperature $\geq 38^{\circ}\text{C}$	Temperature $\geq 38^{\circ}\text{C}$	Temperature $\geq 38^{\circ}\text{C}$ With
Hypotension ^b	None	Not requiring vasopressors	Requiring a vasopressor with or without vasopressin	Requiring multiple vasopressors (excluding vasopressin) And/or ^b
Hypoxia	None	Requiring low-flow nasal cannula ^c or blow-by	Requiring high-flow nasal cannula ^c , facemask, nonrebreather mask, or Venturi mask	Requiring positive pressure (eg, CPAP, BiPAP, intubation and mechanical ventilation)

Organ toxicities associated with CRS may be graded according to CTCAE v5.0 but they do not influence CRS grading.

a Fever is defined as temperature $\geq 38^{\circ}\text{C}$ not attributable to any other cause. In patients who have CRS then receive antipyretic or anticytokine therapy such as tocilizumab or steroids, fever is no longer required to grade subsequent CRS severity. In this case, CRS grading is driven by hypotension and/or hypoxia.

b CRS grade is determined by the more severe event: hypotension or hypoxia not attributable to any other cause. For example, a patient with temperature of 39.5°C , hypotension requiring 1 vasopressor, and hypoxia requiring low-flow nasal cannula is classified as grade 3 CRS.

c Low-flow nasal cannula is defined as oxygen delivered at ≤ 6 L/minute. Low flow also includes blow-by oxygen delivery, sometimes used in pediatrics. High-flow nasal cannula is defined as oxygen delivered at > 6 L/minute.

Abbreviations: ASTCT=American Society for Transplantation and Cellular Therapy; BiPAP=Bi-level positive airway pressure CPAP= Continuous Positive Airway Pressure; CRS=Cytokine release syndrome.

Source: (1)

10.12 APPENDIX 12 GUIDELINES FOR THE MANAGEMENT OF TUMOR LYSIS SYNDROME (TLS)

TLS is a metabolic derangement that is the result of rapid destruction of tumor cells. TLS is common in hematological malignancies and can cause several side effects; some of them may become life-threatening. Early recognition of TLS and initiation of therapy is essential.

Intravenous hydration is recommended for all participants prior to start of SAR444245 infusions and is left to Investigator judgment for further cycles.

The participants at greatest risk of TLS are those with a high tumor burden prior to treatment. These patients should be monitored closely, and appropriate precautions should be taken (such as use of prophylactic uric acid lowering agents (eg, allopurinol or rasburicase) and regular measurement of electrolytes.

This appendix provides parameters to be checked in case of TLS suspicion and recommendations for TLS management. Abnormalities listed in this appendix do not exclusively support TLS diagnosis and any differential diagnosis also needs to be assessed, if appropriate.

TLS may present with laboratory parameters changes, clinical manifestations, or both as indicated in [Table 13](#).

Table 13 - Tumor lysis syndrome definitions**Table I. Cairo-Bishop definition of laboratory tumour lysis syndrome.**

Uric acid	$x \geq 476 \text{ } \mu\text{mol/l}$ or 25% increase from baseline
Potassium	$x \geq 6.0 \text{ mmol/l}$ or 25% increase from baseline
Phosphorous	$x \geq 2.1 \text{ mmol/l}$ (children), $x \geq 1.45 \text{ mmol/l}$ (adults) or 25% increase from baseline
Calcium	$x \leq 1.75 \text{ mmol/l}$ or 25% decrease from baseline

Modified from Hande and Garrow (1993).

Laboratory tumour lysis syndrome (LTLS) is defined as either a 25% change or level above or below normal, as defined above, for any two or more serum values of uric acid, potassium, phosphate, and calcium within 3 d before or 7 d after the initiation of chemotherapy. This assessment assumes that a patient has or will receive adequate hydration (\pm alkalinization) and a hypouricaemic agent(s).

Table II. Cairo-Bishop definition of clinical tumour lysis syndrome.

- (1) Creatinine*: $x \geq 1.5 \text{ ULN}^\dagger$ (age >12 years or age adjusted)
- (2) Cardiac arrhythmia/sudden death*
- (3) Seizure*

Modified from Hande and Garrow (1993).

Clinical tumour lysis syndrome (CTLS) assumes the laboratory evidence of metabolic changes and significant clinical toxicity that requires clinical intervention. CTLS is defined as the presence of LTLS and any one or more of the above-mentioned criteria.

*Not directly or probably attributable to a therapeutic agent (e.g. rise in creatinine after amphotericin administration).

† Creatinine levels: patients will be considered to have elevated creatinine if their serum creatinine is 1.5 times greater than the institutional upper limit of normal (ULN) below age/gender defined ULN. If not specified by an institution, age/sex ULN creatinine may be defined as: $> 1 < 12$ years, both male and female, $61.6 \text{ } \mu\text{mol/l}$; $\geq 12 < 16$ years, both male and female, $88 \text{ } \mu\text{mol/l}$; ≥ 16 years, female, $105.6 \text{ } \mu\text{mol/l}$; ≥ 16 years, male, $114.4 \text{ } \mu\text{mol/l}$.

For participants in the safety run-in or participants who are hospitalized because of high tumor burden or at Investigator's discretion, tumor lysis laboratory tests (corrected calcium, magnesium, phosphate, uric acid, and lactate dehydrogenase [LDH] levels) will be obtained per details provided in the individual substudy).

Cardiac monitoring and admission to the ICU is required if TLS is established, as well as continuing laboratory monitoring every 4-6 hours. Additional measures to treat metabolic derangements associated with TLS may be required, as shown in [Table 14](#).

Prophylaxis against TLS may be required depending on the patient's risk for TLS, as described below.

Low-risk is defined as:

- Patients with low tumor burden (WBC $\leq 50 \times 10^9/l$ and normal LDH level)
- Patients receiving low intensity cytoreductive therapy
- Normal pre-existing uric acid
- Adequate hydration
- No tumor infiltration in the kidney

High-risk is defined as:

- Hematological malignancies with high proliferative rate
- High tumor burden (WBC $\geq 50 \times 10^9/l$ and high LDH level)
- Elevated uric acid level
- Patients receiving intensive cytoreductive therapy
- Poor hydration
- Leukemia infiltration of the kidney

Recommendations for **intravenous hydration** during SAR444245 treatment in patients at high risk for TLS, include the following:

- [REDACTED]
- [REDACTED]
- [REDACTED]
- [REDACTED]

For high risk patients, prophylactic treatment with **allopurinol** should begin 2 to 3 days before the start of antineoplastic therapy and continue for 10 to 14 days, as described in [Table 15](#).

Rasburicase is indicated for patients with the following features:

- High-risk of TLS development
- Urgent need to initiate therapy in a patient with a high bulk of malignant disease
- In a situation where adequate hydration may be difficult or impossible
- Acute renal failure

The dose for rasburicase is indicated in [Table 15](#). Redosing must be individualized.

Recommendations regarding the selection of allopurinol and/or rasburicase are summarized in [Table 16](#).

Table 14 - Specific recommendations for treatment of TLS

Hyperphosphatemia: ≥ 2.1 mmol/L	Removing phosphates from i.v. solutions Oral phosphate binders: e.g. aluminum hydroxide orally at 50-150 mg/kg/24 h q6h Peritoneal dialysis, hemodialysis or continuous venovenous hemofiltration may be required in a case of severe hyperphosphatemia. Calcium infusion is prohibited!
Hypocalcemia: ≤ 1.75 mmol/L (serum) or ionized calcium is \leq of ionized local limit	Treatment not required if asymptomatic. Symptomatic hypocalcemia (muscle cramps and spasms, paresthesias, arrhythmias, heart block, hypotension, confusion, delirium, hallucination, seizures) requires treatment: Calcium gluconate 50 – 100 mg/kg/dose i.v.
Hyperkalemia	Moderate and asymptomatic (≥ 6.0 mmol/L): Avoid i.v. and oral potassium ECG and cardiac rhythm monitoring Sodium polystyrene sulphonate 1 g/kg with 50 % sorbitol po or per rectum Severe (>7.0 mmol/L) and/or symptomatic Same as above, plus Calcium gluconate (100–200 mg/kg) i.v. and/or Regular insulin (0.1 unit/kg i.v.) + D25 (2 mL/kg) i.v. Dialysis
Renal dysfunction (uremia)	Fluid and electrolyte management Uric acid and phosphate management Adjust renally excreted drug doses Dialysis (hemo- or peritoneal) Hemofiltration (CAVH, CVVH, CAVHD or CVVHD)
Hyperuricemia: uric acid ≥ 476 μmol/L	See Table 15 and Table 16 regarding selection and dose of hypouricemic agents: Allopurinol Rasburicase (recombinant urate oxidase).

Table 15 - Recommendations on the use of hypouricemic agents**Allopurinol**

100 mg/m²/dose q8 h (10 mg/kg/d divided q8 h) p.o.
(maximum 800 mg/d) or 200–400 mg/m²/d in 1–3 divided doses i.v. (maximum 600 mg/d)
Reduce dose by 50% or more in renal failure
Reduce 6-mercaptopurine and/or azathioprine doses by 65–75% with concomitant allopurinol
Adjust doses of drugs metabolized by P450 hepatic microsomal enzymes with concomitant allopurinol

Rasburicase

Avoid in glucose-6-phosphate dehydrogenase deficient patients.
Immediate and permanent stop of treatment if methemoglobinemia is result.
0.05–0.20 mg/kg i.v. over 30 min
To measure uric acid levels place blood sample immediately on ice to avoid continual pharmacological ex vivo enzymatic degradation.
10% incidence of antibody formation.

Table 16 - Recommendations on selection of hypouricemic agents

	Allopurinol	Rasburicase
Uric acid level	Normal	Elevated
Tumor type	Non-hematological Hodgkin's lymphoma, CML	Burkitt's lymphoma, lymphoblastic lymphoma, ALL, AML
	Tumor burden	
WBC count	≤50 · 10 ⁹ /L	>50 · 10 ⁹ /L
LDH	≤ 2 · normal	>2 · normal
Cytoreductive intensity	Mild	Aggressive
Kidney tumor infiltration	Absent	Present

10.13 APPENDIX 13: ECOG PERFORMANCE STATUS AND LANSKY SCALE**Table 17 - ECOG PERFORMANCE STATUS**

Grade	ECOG
0	Fully active, able to carry on all pre-disease performance without restriction
1	Restricted in physically strenuous activity but ambulatory and able to carry out work of a light or sedentary nature, e.g., light house work, office work
2	Ambulatory and capable of all selfcare but unable to carry out any work activities. Up and about more than 50% of waking hours
3	Capable of only limited selfcare, confined to bed or chair more than 50% of waking hours
4	Completely disabled. Cannot carry on any selfcare. Totally confined to bed or chair
5	Dead

Source: (36).

Table 18 - Lansky Play/Performance Status

A. Normal range of play
Able to carry on usual play activities both active and quiet; child initiates play; no special adult assistance or direction needed; participation in interactive play

 • 100 Fully active • 90 Minor restrictions in physically strenuous play • 80 Restricted in physically strenuous play (eg. chasing games); may tire more easily, otherwise active
B. Mild to moderate restriction of play
Able to engage in some active play, but spends greater than usual time in quiet play; requires varying degree of assistance in setting up and completing play; restricted in interactive play

 • 70 Both greater restriction of, and less time spent in, active play • 60 Ambulatory 50% of time; limited active play with adult assistance, supervision • 50 Considerable adult assistance required for any active play; fully able to engage in quiet play (set up games, turn on TV, etc.)

A. Normal range of play

Able to carry on usual play activities both active and quiet; child initiates play; no special adult assistance or direction needed; participation in interactive play

- 100 Fully active
- 90 Minor restrictions in physically strenuous play
- 80 Restricted in physically strenuous play (eg. chasing games); may tire more easily, otherwise active

C. Moderate to severe restriction of play

No active play; play limited to quiet activities; requires varying degree of assistance for quiet play

- 40 Able to initiate most quiet activities
- 30 Needs considerable assistance even for quiet activities
- 20 Play entirely limited to very passive activities initiated by other (eg. TV)
- 10 Completely disabled, no play
- 0 Unresponsive

Source: (37).

For participants < 16 years old.

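### Appendix 12, Table 14 bans calcium infusion in hyperphosphatemia but requires IV calcium for symptomatic hypocalcemia, and one tumor lysis patient can meet both rows (minor wording contradiction)

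*Protocol*

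**What the plan says.** Master protocol Section 10.12 (Appendix 12), Table 14, has five rows: hyperphosphatemia, hypocalcemia, hyperkalemia, renal dysfunction and hyperuricemia. Three of them mention calcium.

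- **Hyperphosphatemia, 2.1 mmol/L or more.** After phosphate removal, binders and dialysis options, the row closes with "Calcium infusion is prohibited". No exception is given.
- **Hypocalcemia, serum calcium 1.75 mmol/L or less, or low ionized calcium.** Without symptoms: "Treatment not required if asymptomatic". With symptoms: "Symptomatic hypocalcemia (muscle cramps and spasms, paresthesias, arrhythmias, heart block, hypotension, confusion, delirium, hallucination, seizures) requires treatment", and the treatment is "Calcium gluconate 50 – 100 mg/kg/dose i.v".
- **Hyperkalemia, above 7.0 mmol/L and/or symptomatic.** The row lists "Calcium gluconate (100–200 mg/kg) i.v. and/or" insulin with dextrose, and then dialysis.

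The appendix describes its own status: "This appendix provides parameters to be checked in case of TLS suspicion and recommendations for TLS management". The TLS sections of the substudies (Substudy 01, Section 6.5.4.7; Substudy 03, Section 6.5.4.6) say that treatment will include correcting calcium, potassium or phosphorus, and send the site to Appendix 12. Neither gives an order of precedence.

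**The concern.** The two strongest directives in the table, a prohibition and a requirement, concern the same treatment and sit in adjacent rows. A site that took the prohibition literally would withhold IV calcium from a patient with, say, a seizure or an arrhythmia, for whom the next row requires it. A site that followed the hypocalcemia row would breach the prohibition. The appendix itself notes that TLS can become life-threatening and that early treatment matters, so its instructions should not need the reader to set one of them aside.

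What is at stake is clarity of emergency care. No endpoint, estimand, sample size or dose rule depends on this table.

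**Working it through.** No statistical calculation applies. The check is whether one patient can meet both rows, and whether any text ranks them.

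**Step 1: can the triggers coincide?** Table 13 defines laboratory TLS by abnormality in at least two of four analytes: uric acid, potassium, phosphate and calcium. Four analytes give 4 × 3 / 2 = 6 possible pairs, and phosphate with calcium is one of them. The protocol therefore foresees the combination.

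**Step 2: do the thresholds line up?**

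| Analyte | Table 13 (laboratory TLS) | Table 14 row trigger |
|---|---|---|
| Phosphate, adults | 1.45 mmol/L or more, or a 25% rise | 2.1 mmol/L or more |
| Phosphate, children | 2.1 mmol/L or more, or a 25% rise | 2.1 mmol/L or more |
| Calcium | 1.75 mmol/L or less, or a 25% fall | 1.75 mmol/L or less, or low ionized calcium |

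The adult criterion in Table 13 ends with "adults) or 25% increase from baseline". An adult can therefore have laboratory TLS with phosphate from 1.45 up to, but not including, 2.1 mmol/L, a band of 2.1 − 1.45 = 0.65 mmol/L, without reaching the prohibition. Laboratory TLS alone does not create the conflict.

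**Step 3: when do the instructions clash?** Take phosphate at or above 2.1 mmol/L and calcium at or below 1.75 mmol/L.

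- No symptoms: the first row forbids calcium and the second does not call for it. There is no conflict.
- Any of the nine symptoms in the hypocalcemia row: the first row forbids calcium infusion and the second requires IV calcium gluconate. The rows conflict.

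Table 13 has three clinical TLS criteria: creatinine, "Cardiac arrhythmia/sudden death", and seizure. Two of the three, arrhythmia and seizure, are also among the nine symptoms that trigger calcium. Patients with clinical TLS are thus a group in whom the clash could arise.

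**Step 4: is the hyperkalemia row in the same position?** Only weakly. Calcium gluconate is joined by and/or to insulin with dextrose, and dialysis is also listed. A site can comply with the prohibition by using the alternatives. Of the five rows, one prohibits calcium, one requires it when symptoms are present, and one offers it as an option.

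**Step 5: does anything rank the rows?** Nothing in the visible text of Appendix 12 or the two substudy TLS sections does. The blacked-out lines in Appendix 12 fall under intravenous hydration for high-risk patients, not under Table 14.

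**The case against.** The best case against acting is that other text already leaves the choice to the clinician.

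- **Discretion over supportive care.** Master protocol Section 6.8 leaves the last word on supportive treatment with the investigator or treating physician. Section 6.8.1 lets the investigator give whatever is judged necessary for the participant's welfare. Section 6.8.2 does not list calcium among prohibited medications and allows other medically necessary drugs. Section 6.5.3 of each substudy leaves corrective therapy for treatment-related events to the investigator's judgment.
- **Setting and status.** Once TLS is established, Appendix 12 calls for intensive care, cardiac monitoring and laboratory checks every 4 to 6 hours. It presents its contents as recommendations and says that the Table 14 measures may be needed.
- **A natural reconciliation.** The hypocalcemia row is the specific rule for low calcium and already separates patients with and without symptoms. The prohibition can be read as applying only to giving calcium in other circumstances. One could also try to separate an infusion from an IV dose.

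The first two arguments stand as reasons why harm is unlikely, and they keep the priority low. They settle who decides, but they do not reconcile the instructions that the person deciding is given. The third is plausible and may well be what was meant, but the documents state neither reading.

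A reader might infer that participants with symptoms would be left untreated. The documents do not support that: a site would have to disregard the discretion that Sections 6.8 to 6.8.2 give it. A reader might also infer that every laboratory TLS case is affected, or that the hyperkalemia row conflicts just as sharply. Steps 2 to 4 of the working show otherwise.

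**Conclusion.** The contradiction is real and the table is wrong as written, but it is minor. It is confined to patients with phosphate at or above 2.1 mmol/L, hypocalcemia as Table 14 defines it, and at least one of nine listed symptoms. How many participants that could be is unknown: the documents give no TLS incidence for SAR444245, and master protocol Section 2.3.1.2.1 says that there are no preclinical TLS data for it. There is no effect on endpoints, dose decisions or analysis.

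The conclusion assumes that the visible text is complete on this point. It does not depend on which row should prevail clinically. The documents do not say, and that is for the sponsor's clinical team.

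**What to change.** Keep the prohibition and add an exception, so that the last line of the hyperphosphatemia row reads: "Calcium infusion is prohibited" except for symptomatic hypocalcemia (see next row). The sponsor's clinical team should confirm this wording and add a clause saying whether calcium gluconate for severe or symptomatic hyperkalemia is also exempt.

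Replacing the prohibition with a rule about asymptomatic hypocalcemia alone would go too far. It would remove the ban for hyperphosphatemic patients whose calcium is normal, and would lift the only stated restriction where hyperphosphatemia and hyperkalemia overlap.

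The cost is one exception and one clause in Table 14, bundled into the next amendment. It does not justify an amendment of its own.
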